# **SAP Revision Log**

[figure not shown]
SAP Section	Brief Description of Revision	Date of Revision
11	Number of concentrations required for computation of AUC	06-FEB-2020
11	Methods of imputation for BQL data	06-FEB-2020

# List of Abbreviations and Definitions of Terms

Term	Description
%BSA	percent body surface area
AD	atopic dermatitis
AE	adverse event
AESI	adverse event of special interest
AhR	aryl hydrocarbon receptor
ALT	alanine aminotransferase
Anti-HBc	anti-hepatitis B core antigen
AST	aspartate aminotransferase
AUC 0-τ	area under the plasma concentration vs time curve in one dosing interval
BMI	body mass index
BP	blood pressure
BSA	body surface area
CFR	Code of Federal Regulations
CI	confidence interval
C max	maximum plasma concentration
CTCAE	Common Terminology Criteria for Adverse Events
CV	cardiovascular
ECG	electrocardiogram
eCRF	electronic case report form
ET	early termination
FSH	follicle-stimulating hormone
HBC	hepatitis C virus
HBsAg	hepatitis B surface antigen
Нер	hepatitis
HIV	human immunodeficiency virus

Term	Description
HR	heart rate
ICF	informed consent form
ICH	International Council for Harmonization
IEC	Independent Ethics Committee
IMP	investigational medicinal product
IRB	Institutional Review Board
IV	intravenous(ly)
LS	least squares
LTS	Local Tolerability Scale
МСН	mean corpuscular hemoglobin
MCHC	mean corpuscular hemoglobin concentration
MCV	mean corpuscular volume
PASI	Psoriasis Area and Severity Index
PGA	Physician Global Assessment
PK	pharmacokinetic(s)
PND	postnatal day
QTcF	QT interval corrected with Fridericia's formula
RBC	red blood cell(s)
SAE	serious adverse event
TEAE	treatment-emergent adverse event
t max	time of maximum plasma concentration
t 1/2	elimination half life
ULN	upper limit of normal
UV	ultraviolet
WBC	white blood cell(s)
WOCBP	women of childbearing potential

### 1. INTRODUCTION

This document outlines the statistical methods to be implemented during the analyses of data collected within the scope of Dermavant Sciences GmbH Protocol DMVT-505-2002 [Open-Label Maximal Use Study to Evaluate the Safety, Tolerability, and Pharmacokinetics of Tapinarof Cream, 1% in Adults with Extensive Plaque Psoriasis]. The purpose of this plan is to provide specific guidelines from which the statistical analyses will proceed. Any deviations from this plan will be documented in the clinical study report (CSR).

### STUDY DOCUMENTS 2.

The following study documents were used for the preparation of the SAP:

- Protocol version 1.0, dated 26-April-2019
- Annotated electronic case report form (eCRF), version 1.4, dated 22-Jul-2019

### 3. STUDY OBJECTIVES

### 3.1 **Primary Objectives**

• To evaluate the safety and tolerability of tapinarof cream, 1% in adult subjects with extensive plaque psoriasis

Associated endpoints including:

- o Frequency and severity of adverse events (AEs) (local and systemic)
- Laboratory and biomarker values
- Vital signs
- Electrocardiograms (ECGs)
- o Mean Local Tolerability Scale (LTS) scores by visit
- To evaluate the pharmacokinetics (PK) of tapinar of cream, 1% in adult subjects with extensive plaque psoriasis

Associated endpoints including:

Tapinarof and tapinarof sulfate (metabolite) plasma PK parameters on Day 1 and Day 29, if data permit, including: area under the plasma concentration vs time curve in one dosing interval (AUC0- $\tau$ ), maximum plasma concentration (Cmax), time of maximum plasma concentration ( $t_{max}$ ) and elimination half-life ( $t_{1/2}$ ).

### **Secondary Objectives** 3.2

• To exclude clinically relevant effects of tapinar of cream, 1% on QT interval corrected by Fridericia's formula (QTcF)

Associated endpoints including:

Analysis of change from Baseline in QTcF ( $\Delta$ QTcF) at each post-treatment time point on the sampling day with the higher Cmax (Day 1 or Day 29)

- Concentration-QTc analysis investigating the relationship between tapinar of plasma concentration and ΔQTcF, if data permit
- To assess the efficacy of tapinarof cream, 1% in adult subjects with extensive plaque psoriasis

Associated endpoints including:

Mean change from Baseline to Day 29 in Physician Global Assessment (PGA),
 Psoriasis Area and Severity Index (PASI), and percent body surface area (%BSA)

### 3.3 Exploratory Objective

### 4. STUDY DESIGN AND PLAN

This is a Phase 2a, multicenter, open-label study to evaluate the safety and PK of topical tapinarof cream in adults with extensive plaque psoriasis. The study will consist of 3 phases: Screening (up to 34 days), Treatment (29 days), and Follow-up (7 to 10 days).

At Day -1, eligible subjects will be enrolled into the study. During the treatment period beginning on Day 1 (Baseline), subjects will apply tapinarof cream, 1% to affected areas once a day for 29 days. Subjects will return to the clinic on Days 2, 15, 29, and 30 for study assessments and will receive a phone call on Days 8 and 22. Subjects will return to the clinic for a follow-up visit 7 to 10 days after the Day 29 visit. On clinic visit days, subjects will apply the study drug under the supervision of site personnel, after assessments have been completed. Full PK profiles and Holter monitoring will be collected on Day 1 and Day 29 (with corresponding 24-hour time points collected on Day 2 and Day 30, respectively). Limited PK sampling will be performed on Day 15. Pre-treatment, time-matched Holter monitoring will be conducted on Day -1 and the morning of Day 1.

Study drug will be dispensed to subjects during the clinic visits and will be administered at home between clinic visits as instructed by site personnel. Subjects will be instructed to apply study drug once daily to all affected areas, including newly appearing plaques and plaques/areas that improve during the study. Subjects will apply sufficient study drug to cover completely each lesion with a thin layer of study drug and will record the time of study drug application in a daily diary provided by the study site. Note that subjects are allowed, but not required, to treat palms, fingernails, soles, toenails, and scalp plaques with study drug. If a subject chooses to treat

Statistical Analysis Plan 06-FEB-2020

plaques on palms, fingernails, soles, toenails, and/or scalp, they should do so for the entirety of the treatment period from Day 1 to Day 29. Subjects will be instructed to apply study drug in the morning throughout the entirety of their participation in the study. At the phone contacts at Day 8 and Day 22, subjects should be reminded to complete their daily diary and bring it with them to the next clinic visit.

Study drug application instructions will be reviewed at all post-baseline clinic visits. On clinic visit days, subjects will be instructed/reminded on how to apply study drug (except during the final treatment/end-of-study visits). During the clinic visits, subjects will apply the daily dose of study drug while on-site under the supervision of site personnel, after other assessments have been completed.

Subjects who withdraw from the study before Day 30 will complete an Early Termination Visit. Study duration for subjects who complete this study is approximately 10 weeks in total. Refer to the study protocol for further details (Section 6 for descriptions of study procedures and assessments and Section 7 and the Schedule of Assessments [Table 1] for timing of procedures and assessments).

### **Treatment Groups and Duration**

All subjects will receive tapinar of cream, 1% for 29 days with once daily application.

A subject will be considered to have completed the study when he/she completes all required procedures/visits for the 29-day treatment phase.

[figure not shown]
### 5. DETERMINATION OF SAMPLE SIZE

This study will be conducted to evaluate the safety and PK of tapinar of cream, 1% in adult subjects with extensive plaque psoriasis. There is no formal statistical hypothesis testing planned and the sample size is mainly based on feasibility and an estimated number of subjects needed to address the objectives of the study.

### 6. GENERAL ANALYSIS CONSIDERATIONS

The statistical analyses will be reported using summary tables, listings, and figures (TLFs). The International Council for Harmonisation (ICH) numbering convention will be used for all TLFs.

Continuous variables will be summarized with means, standard deviations, medians, minimums, and maximums. Categorical variables will be summarized by counts and by percentage of subjects in corresponding categories. Percentages are based on the number of non-missing results unless otherwise mentioned. Percentages showing a rate relative to the total number of subjects in this group are given in special tables (e.g., AE tables). Footnotes will specify the percent basis in those cases.

All analyses and tabulations will be performed using SAS® software Version 9.4 or higher. Tables, listings, and figures will be presented in RTF format.

The process for SAS program validation and quality control (QC) for programs and outputs is documented in the Synteract working instruction "SAS programming quality control." Study-specific QC requirements can be found in Appendix B: SAS Programming QC Requirements.

Unless otherwise specified, the Baseline value for each variable is the last non-missing value prior to the initiation of study drug. No imputations will be made for missing values. Summaries will be based on observed data only. Unscheduled visits will not be summarized but will be included in the listings.

Conventions for handling partial dates and missing dates for AEs and prior and concomitant medications are given below. Listings will present the dates in their original format (without any imputation).

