 - elimination half-life $(t_{1/2})$

- Analysis of change from Baseline in QTcF (Δ QTcF) at each post-treatment time point on the sampling day with the higher C_{max} (Day 1 or Day 29)
- Concentration-QTc analysis investigating the relationship between tapinar of plasma concentration and ΔQTcF, if data permit
- Mean change from Baseline to Day 29 in PGA, PASI, and %BSA

Statistical Methods:

Safety and PK data will be presented in tabular and/or graphical format and summarized descriptively.

For cardiodynamic ECG assessments, the primary analysis will be based on by-time point analysis to evaluate the effect of tapinarof cream, 1% on the $\Delta QTcF$ at each post-dosing time point using the Intersection Union Test. The effect of tapinarof on ΔHR , ΔPR , and ΔQRS will also be evaluated using the Intersection Union Test. An analysis of categorical outliers will also be performed for changes in HR, PR, QRS, QTcF, T-wave morphology and U-wave presence. In addition, a potential concentration-QTc analysis will be performed if a sufficient number of PK samples are measurable, i.e., above the lower limit of quantification, to provide a PK profile in most subjects. In this concentration-QTc analysis, the relationship between tapinarof plasma concentrations and $\Delta QTcF$ will be evaluated using a linear mixed-effects modeling approach.

PGA, PASI, and %BSA will be compared to Baseline values using a one sample t-test.

SCHEDULE OF ASSESSMENTS

Table 1: Schedule of Assessments

		Treatment Period (Tapinarof Cream, 1% Once Daily)						Follow-up		
Procedure	Screening (up to 34 days prior to Day 1)	Day -1	Baseline Day 1	Day 2	Day 8	Day 15	Day 22	Day 29	Day 30	(7-10 days after Day 29) or ET
	Visit 1	Visit 2	Visit 3	Visit 4	Phone Call	Visit 5	Phone Call	Visit 6	Visit 7	Visit 8
Informed consent	X									
Inclusion and exclusion criteria	X	X	X							
Demography	X									
Brief physical exam (including height, weight and BMI at Screening)	X									X
Medical history (including year of psoriasis diagnosis)	X									
Pregnancy test (WOCBP)	X		X							X
PGA, PASI, and % BSA evaluation ^a	X		X					X		
HIV, Hep B and Hep C Screen	X									
Laboratory assessments (chemistry including liver chemistries, hematology, urinalysis)	X		X					X		X
LTS assessment by Investigator			X			X		X		
Single 12-lead ECG	X									X
Continuous Holter Monitoring		X ^b	X ^c	X ^d				X ^c	X ^d	
Vital signs (pre-dose; HR, BP, and temperature)	X		X							X
Randomization			X							

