4.6.1. Reasons for Withdrawal from the Study

Study drug will be discontinued for any of the following reasons:

- Subject has an AE that is considered to be related to study drug or procedures AND is severe enough to warrant treatment discontinuation, as determined by the Investigator
- Subject requires concurrent prohibited medication during the study. If, in the opinion of the Investigator and the study Medical Monitor, such medication will not interfere with the conduct or interpretation of the study or compromise the safety of the subject, then the subject may continue to receive study drug.
- Pregnancy
- Any Grade 3 or 4 AE considered causally related to study drug

Study drug may be discontinued for any of the following reasons:

- Subject noncompliance
- Investigator noncompliance
- Discontinuation of the study at the request of the Sponsor, regulatory agency, or an Institutional Review Board (IRB)/Independent Ethics Committee (IEC).

If a subject meets a withdrawal criterion during treatment, an Early Termination Visit will be required (Section 7.10).

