4.6.2. Withdrawal Procedures

The primary reason for the discontinuation of study drug and/or withdrawal from study must be recorded in the source document and on the electronic case report form (eCRF). If a subject is prematurely discontinued from study drug, the Investigator must make every effort to perform an Early Termination Visit (Section 7.10) and document the primary reason for withdrawal.

Should a subject fail to attend a required study visit, the site should attempt to contact the subject and reschedule the missed visit as soon as possible. The site should also counsel the subject on the importance of maintaining the assigned visit schedule and ascertain whether the subject wishes to and/or should continue in the study based on previous noncompliance. In cases where the subject does not return for the rescheduled visit or cannot be reached to reschedule the missed visit, the site should make every effort to regain contact with the subject so that they can appropriately be withdrawn from the study with a primary reason of "Lost to Follow-up."

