7.10. Visit 8; Follow-Up (7-10 days After Day 29)/Early Termination

Follow-up/Early Termination assessments are as follows:

- ECG recording
- Urine pregnancy test (WOCBP only)
- Brief physical examination
- Vital signs measurements
- Blood and urine sample collection for clinical laboratory tests
- AE recording
- Concomitant medication recording

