8.1.1. Definition of Adverse Events

An AE is any untoward medical occurrence in a subject temporally associated with the use of a study drug, whether considered causally related or not related to the study drug.

An AE can therefore be any unfavorable and unintended sign (including an abnormal laboratory finding), symptom, or disease (new or exacerbated) temporally associated with the use of a study drug.

Events meeting the definition of an AE include:

- Any abnormal laboratory test results (e.g., hematology, clinical chemistry) or other safety assessments (e.g., vital signs measurements), including those that worsen from Baseline, and felt to be clinically significant in the medical and scientific judgment of the Investigator;
- Exacerbation of a chronic or intermittent pre-existing condition (e.g., atopic dermatitis) including either an increase in frequency and/or intensity of the condition;
 - For skin-related AEs, it should be noted whether or not the event is in the area of active application of study drug, and/or if spreading beyond the application site.
- New conditions detected or diagnosed after study drug administration even though it may have been present prior to the start of the study;
- Signs, symptoms, or the clinical sequelae of a suspected interaction;
- Signs, symptoms, or the clinical sequelae of a suspected overdose of either study drug or a concomitant medication (overdose per se will not be reported as an AE/SAE);
- "Lack of efficacy" or "failure of expected pharmacological action" per se will not be reported as an AE or SAE. However, the signs, symptoms, and/or clinical sequelae resulting from lack of efficacy will be reported as AE or SAE if they fulfill the definition of an AE or SAE.
- Evaluation of local tolerability at the site of topical application (e.g., burning/stinging, pruritus, and erythema).

Events that **do not** meet the definition of an AE include:

- Any clinically significant abnormal laboratory findings or other abnormal safety assessments that are associated with the underlying disease, unless judged by the Investigator to be more severe than expected for the subject's condition;
- The disease/disorder being studied or expected progression, signs, or symptoms of the disease/disorder being studied, unless more severe than expected for the subject's condition:
- Medical or surgical procedure (e.g., endoscopy, appendectomy); the condition that leads to the procedure is an AE.

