8.1.4. Adverse Events of Special Interest

In prior clinical studies, the following AEs have been identified as AEs of particular clinical importance and will be reported as AESIs in this study; in each case study drug may be discontinued, based upon Investigator's judgment, and the subject may be discontinued from the study.

- Contact dermatitis: the study site should collect location, duration, size, associated symptoms (itching, burning, pain), severity (mild, moderate, or severe), and photograph the affected site (if possible). If subject contacts the study site to report significant skin irritation at or near the site of study drug application between study visits, the subject should be brought for an unscheduled visit, if possible.
- Folliculitis: the study site should collect the location, duration, size, associated symptoms (itching, burning, pain), severity (mild, moderate, or severe), indicate whether pustular, and photograph the affected site (if possible).
- Headache: site should collect duration, severity (mild, moderate, or severe), onset, and location.

For each AESI, a narrative may be written and included in the Clinical Study Report.

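### Subjects who stop before Day 29 have no LTS, PGA, PASI or %BSA at early termination and so leave the Day 29 summaries

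*SAP*

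**What the plan says.** **Collection.** In Protocol Table 1 the row "LTS assessment by Investigator" is marked on Days 1, 15 and 29 only. The row for PGA, PASI and %BSA is marked at Screening, Day 1 and Day 29 only. Section 7.10 opens with "Follow-up/Early Termination assessments are as follows" and lists ECG, urine pregnancy test, brief physical examination, vital signs, laboratory samples, AEs and concomitant medication. None of the four scales is there. Section 4.6.2 nevertheless expects the visit to take place: "If a subject is prematurely discontinued from study drug, the Investigator must make every effort to perform an Early Termination Visit".

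**Analysis.** SAP Section 6 makes no imputation for missing values and says: "Summaries will be based on observed data only. Unscheduled visits will not be summarized but will be included in the listings". On denominators it says: "Percentages are based on the number of non-missing results unless otherwise mentioned". SAP 10.7 summarises LTS at Baseline and Days 15 and 29. SAP 9 summarises change to Day 29 and the percentage with treatment success at Day 29. Neither section maps early-termination values to Day 29 or says how a missing Day 29 value counts.

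**Stopping.** Protocol 4.6.1 stops study drug for "Any Grade 3 or 4 AE considered causally related to study drug" and sends subjects who meet a withdrawal criterion to the early-termination visit. Protocol 8.1.4 names contact dermatitis, folliculitis and headache as AEs of special interest and adds that "in each case study drug may be discontinued".

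**The concern.** Mean LTS score by visit is one of the listed primary endpoints (Protocol Section 2, SAP 3.1), and the product is a cream whose tolerability is a primary objective. AEs, laboratory values, vital signs and ECGs, the other safety endpoints on that list, are all collected at early termination; LTS is not.

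The subjects most likely to be missing at Day 29 include those who stopped because of a local reaction. If so, the Day 15 and Day 29 LTS means describe those who tolerated the cream well enough to continue, and look better than experience on treatment. The secondary efficacy endpoints, mean change to Day 29 in PGA, PASI and %BSA, lose the same subjects, as does the success percentage. With about 20 subjects, each one lost is 5% of the data.

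**Working it through.** The plan states no dropout rate, expected LTS values or power, so there is no figure of its own to reproduce. The check traces the schedule and then works an illustration.

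**Trace: what a subject contributes after Baseline**

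| Last visit is early termination | LTS Day 15 | LTS Day 29 | PGA, PASI, %BSA Day 29 |
|---|---|---|---|
| Before Day 15 | none | none | none |
| After Day 15, before Day 29 | yes | none | none |

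No rule in SAP 6, 9 or 10.7 fills these cells. An LTS score taken at an unscheduled visit for skin irritation, which Protocol 8.1.4 foresees, would be listed but not summarised.

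**Inputs to the illustration.** N = 20 is the approximate planned number (Protocol 4.1). The number of stoppers d = 1 or 2 and the number of observed successes s = 6 are assumptions.

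**How likely is any stopper?** With d ~ Binomial(20, p):

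- p = 5%: expected 1; P(at least one) = 1 − 0.95^20 = 64%; P(four or more) = 2%.
- p = 10%: expected 2; P(at least one) = 1 − 0.90^20 = 88%; P(four or more) = 13%.

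**Success percentage.** Reported = s/(N − d). All treated, stoppers as non-successes = s/N. All treated, stoppers as successes = (s + d)/N.

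| d | Reported | Stoppers not successes | Stoppers all successes |
|---|---|---|---|
| 1 | 6/19 = 31.6% | 6/20 = 30.0% | 7/20 = 35.0% |
| 2 | 6/18 = 33.3% | 6/20 = 30.0% | 8/20 = 40.0% |

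The reported rate is 1.6 to 3.3 points too high under the first reading of the missing outcomes and 3.4 to 6.7 points too low under the second. The exact 95% CI for 6/20 is 11.9% to 54.3%, so every one of these differences is well inside sampling error.

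**Mean LTS** (0-4 in Protocol Table 4). The all-treated mean exceeds the reported mean by (d/N) × (stopper mean − completer mean):

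- 1-point difference: 1/20 × 1 = 0.05 and 2/20 × 1 = 0.10.
- 4-point difference, the extreme of the scale: 1/20 × 4 = 0.2 and 2/20 × 4 = 0.4.

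**Mean change.** If completers averaged −50% on PASI and stoppers 0% (both assumed), the all-treated mean would be −50 × 19/20 = −47.5% with one stopper and −50 × 18/20 = −45.0% with two.

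**The case against.** **Poor tolerability in stoppers is recorded elsewhere.** This stands. The AE definition includes "Evaluation of local tolerability at the site of topical application" (Protocol 8.1.1). Contact dermatitis and folliculitis are followed in detail as AEs of special interest. TEAEs are tabulated by severity and for drug discontinuation, disposition gives the reason for stopping, and LTS scores are listed by subject. The gap is confined to the by-visit summaries. But the LTS mean is a primary endpoint in its own right, and SAP 10.4 does not summarise the AEs of special interest separately.

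**The direction is not certain.** This also stands. Stops can be administrative, a related Grade 3 or 4 AE need not be local, and LTS is meant as an average over application sites, so a localised reaction may move it little. The 4-point case needs every stopper at 4 and every completer at 0.

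**SAP 9 bases efficacy on the safety analysis set, so the success denominator may already be all treated subjects.** That wording names a population; it does not displace the non-missing percentage basis in SAP 6. One sentence would remove the doubt.

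**Stopping drug need not mean missing Day 29.** Protocol 4.6 does separate the two, but nothing keeps a subject who has stopped on the Day 29 schedule, and 4.6.1 directs those who meet a withdrawal criterion to early termination.

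**Stoppers may be replaced (Protocol 4.6).** Replacement changes the illustrative figures: with two replaced, 6/20 = 30.0% against 6/22 = 27.3%, a gap of 2.7 points instead of 3.3. It does not recover the lost outcomes.

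**The by-visit means stay as they are under the remedy.** True. The added LTS summary puts the stoppers' scores next to those means and does not re-estimate them.

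**Conclusion.** The point holds. A subject whose last visit is an early-termination visit before Day 29 contributes nothing to the Day 29 LTS, mean-change or success summaries, and one who stops before Day 15 has no post-baseline LTS in any summary. This is a design choice that can be improved cheaply; it is not a contradiction in the plan.

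The size cannot be stated, because it depends on how many subjects stop and how they fared. The worked figures rest on an assumed 1-2 stoppers, 6 successes and no replacement. On those assumptions the effect on the success rate is a few points in either direction and is dwarfed by sampling error. That rate is a descriptive addition (SAP 12), and no decision in the documents depends on it. The case for change rests mainly on LTS, where the missing scores may be the ones that matter most for tolerability.

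**What to change.** 1. **Protocol Table 1 and Section 7.10:** add LTS, PGA, %BSA and PASI to the early-termination visit for subjects who stop before Day 29. Record the date of last application with them, so that on-drug and off-drug scores can be told apart.
2. **SAP 10.7:** add a descriptive summary of each subject's worst post-baseline overall LTS score, including early-termination and unscheduled scores, beside the unchanged by-visit means. If dryness, erythema and peeling are scored separately, give one worst value per item.
3. **SAP 9:** report Day 29 treatment success over all subjects in the safety analysis set, counting a missing Day 29 PGA as not a success, with the observed-case rate alongside. Keep the mean changes in PGA, PASI and %BSA as observed-case with n shown, and list the early-termination values.

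**Cost.** A few minutes of scoring at an existing visit that already includes a skin examination, a small change to the eCRF, one extra LTS summary and one sentence on the denominator. Items 2 and 3 need only SAP changes and can be applied to whatever data are already collected.

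**Downsides.** The all-treated success rate will be slightly lower and will count administrative stops as non-successes, which is why the observed-case rate stays beside it. Some early-termination scores will be off drug, which is why the last-application date is needed.

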6.3.4. Clinical Safety Laboratory Assessments

All protocol-required laboratory assessments must be conducted in accordance with the Study Reference Manual or Laboratory Manual and the protocol Schedule of Assessments (Table 1). Laboratory requisition forms must be completed, and samples must be clearly labeled with the subject number, protocol number, site/center number, and visit date. Details for the preparation and shipment of samples will be provided by the laboratory and are detailed in the Study Reference Manual or the Laboratory Manual. Reference ranges for all safety parameters will be provided to the site by the laboratory responsible for the assessments.

A list of clinical laboratory tests and parameters is provided in Table 3.

All laboratory tests with values that are considered clinically significantly abnormal during participation in the study should be repeated until the values return to normal or Baseline. If such values do not return to normal within a period judged reasonable by the Investigator, the etiology should be identified, if possible, and the Sponsor notified.

Table 3: Laboratory Tests

Diagnostic Screening Tests								
HBsAg Pregnance	 HBsAg Pregnancy Tests: (serum at Screening and urine at other visits; WOCBP only) 							
HBC antibody FSH (as	FSH (as needed in women of non-childbearing only)							
Anti-HBc At the Investigator's discretion, subjects may be screened for alcohol and illicit drug use.								
Serum Chemistry								
• BUN	 Total carbon dioxide 	 Uric acid 						
Creatinine	• Calcium	 Total bilirubin 						
Glucose (fasting not required)	• AST	(+fractionated if						
• Sodium	• ALT	required)						
Potassium	 Alkaline phosphatase 	Total protein						
Chloride		 Albumin 						
Hematology								
Platelet count	• RBC Indices:	WBC Differential:						
RBC count	MCV	Neutrophils						
WBC count (absolute)	MCH	Lymphocytes						
Reticulocyte count	MCHC	Monocytes						
Hemoglobin	Reticulocyte percentage	Eosinophils						
Hematocrit		Basophils						
Routine Urinalysis								
Specific gravity	• Dipstick:							
Microscopic examination	pH							
(if blood or protein is abnormal	Glucose							
abnormai	Protein							
	Blood							
	Ketones							

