8.2.1.2.2. Grade 3 Adverse Event

Subjects who develop a Grade 3 AE should be managed as follows:

- If the Investigator has compelling evidence that the Grade 3AE has not been caused by study drug, then dosing may continue after discussion with the Medical Monitor.
- Subjects who develop a Grade 3 AE that the Investigator considers related to study drug should have the study drug discontinued. Subjects experiencing Grade 3 AEs requiring permanent discontinuation of study drug should be followed weekly until resolution or stability of the AE and encouraged to have early termination assessments completed as outlined in Section 7.10.

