### 10.5 Clinical Laboratory Evaluation

Laboratory assessments (chemistry, hematology and urinalysis) and serologic biomarker tryptase assessment will be summarized using descriptive statistics at Baseline and at each post-baseline time point of collection (see Table 1 Schedule of Events in the protocol). Change from Baseline will also be summarized.

Shift tables for laboratory assessments with low-normal-high at baseline versus low-normal-high at follow-up for the continuous laboratory assessments will be summarized to include low to low, low to normal, low to high, normal to low, normal to normal, normal to high, high to low, high to normal, and high to high at Day 29 and at follow-up (7-10 days after Day 29 or ET).

In addition, laboratory and assessments will be listed by subject.

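### A laboratory or vital-sign abnormality seen only at an unscheduled test cannot enter the shift and abnormal-change tables, because SAP 6 leaves unscheduled visits out of summaries and no worst-post-baseline table is planned (minor)

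*SAP*

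**What the plan says.** SAP 6 (General Analysis Considerations) sets one rule for the whole analysis: "Unscheduled visits will not be summarized but will be included in the listings". It has no exception for safety data.

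SAP 10.5 plans laboratory shift tables "at Day 29 and at follow-up (7-10 days after Day 29 or ET". SAP 10.6 summarizes vital signs at Baseline and follow-up, with shift categories and two levels of abnormal change. SAP Appendix C lists the corresponding shift tables (14.3.4.1.2, 14.3.4.2.2, 14.3.4.3.2 and 14.3.5.1.2). None of these places provides for a worst or any-post-baseline value.

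The protocol can produce values outside the schedule. Under Protocol 6.3.4, laboratory tests with clinically significant abnormal values "should be repeated until the values return to normal or Baseline". Under Protocol 8.1.4, when a subject reports significant skin irritation between visits, "the subject should be brought for an unscheduled visit, if possible". Under Protocol 8.2.1.2.2, subjects with Grade 3 events requiring permanent discontinuation "should be followed weekly until resolution or stability of the AE", and Protocol 8.2.1.2.3 says the same for Grade 4. Protocol 6.4 asks for close monitoring of laboratory abnormalities after an overdose.

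**The concern.** Laboratory values and vital signs are listed among the primary safety endpoints (Protocol 2, SAP 3.1). Values obtained off-schedule are often obtained because something looked wrong. A rule that keeps exactly those values out of the tables is not neutral, because where it has an effect it moves the tables toward no change.

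The scheduled sampling leaves room for this. Protocol 1.2 expects the highest plasma concentrations in the first week of treatment, and Table 1 schedules no post-dose laboratory or vital-sign assessment in that week. Protocol 1.3.1.2 reports nonclinical liver findings and reversible falls in arterial blood pressure, and names laboratory and vital-sign monitoring among the mitigations. A reader of the shift tables would not learn of an abnormality in either area that was caught only by an ad hoc test and had resolved by the next scheduled one.

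**Working it through.** The plan gives no figure to reproduce: the sample size rests on feasibility (Protocol 10.2), and no rate of unscheduled tests is stated. The check sets the schedule against the summary rules. The arithmetic that follows is for scale only.

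**Scheduled points (Protocol Table 1).**

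| | Scheduled visits | Post-baseline points summarized | On-treatment points for a completer |
|---|---|---|---|
| Laboratory | Screening, Day 1, Day 29, Follow-up/ET | 2 | 1 (Day 29) |
| Vital signs | Screening, Day 1 (pre-dose), Follow-up/ET | 1 | 0 |

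Any laboratory value after the Day 1 sample and before Day 29, and any vital sign taken during treatment, is off-schedule and outside the summaries unless it belongs to an early-termination (ET) visit.

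**Which protocol rules can produce a value that is missed.**

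- *Laboratory repeats (6.3.4).* The trigger is an abnormal value already found. If that is the Day 1 pre-dose sample, it is baseline. If it is Day 29 or follow-up, it is already tabulated. A loss occurs only when the repeat is worse than its trigger. The rule covers laboratory tests and does not mention vital signs.
- *Unscheduled visit for skin irritation (8.1.4).* No laboratory test or vital sign is required there, and the event itself is counted as a TEAE.
- *Weekly follow-up after Grade 3 or 4 events (8.2.1.2.2, 8.2.1.2.3), and overdose monitoring (6.4).* These can lead to ad hoc tests, and their results would be off-schedule.
- *Time points added by Note to File (Protocol 7).* The SAP does not say whether these count as scheduled.

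**What one subject is worth.** Input: about 20 subjects (Protocol 4.1). Suppose x subjects have an abnormality seen only off-schedule and no other subject has one.

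- The planned tables show 0/20. The exact one-sided 95% upper bound is 1 − 0.05^(1/20) = 13.9%.
- A worst-value row shows x/20. The upper bound is the 95th percentile of Beta(x+1, 20−x).
  - x = 1: 1/20 = 5.0%, upper bound 21.6%.
  - x = 2: 2/20 = 10.0%, upper bound 28.3%.

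**How much Day 29 alone would catch.** Assume onsets are spread evenly over the 28 days from Day 1 to Day 29 and each abnormality lasts d days. The share still present at Day 29 is d/28.

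- d = 3: 3/28 = 11%.
- d = 7: 7/28 = 25%.
- d = 14: 14/28 = 50%.

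These shares describe the visit schedule. They become relevant to the SAP rule only when someone happens to test in between.

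**The case against.** A reader might infer that the worst laboratory and vital-sign values cannot appear in the safety tables at all. The documents do not support that. Laboratory values at Day 29 and follow-up/ET are summarized with minimum, maximum and shifts, and follow-up vital signs likewise. The worst value is lost only when it falls at an unscheduled test.

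A reader might also infer that every safety summary is affected. That is not so either. Abnormal results that the Investigator considers clinically significant are adverse events (Protocol 8.1.1), and the TEAE tables count subjects whatever the visit (SAP 10.4). A clinically significant liver-test rise found off-schedule would be counted there.

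Further points against the concern are sound. The two protocol rules that come first to mind, laboratory repeats and the skin-irritation visit, seldom create a missed value, as the route-by-route check shows. Nothing is discarded: Listings 16.2.8.1 to 16.2.8.3 and 16.2.9.1 carry the data, and with about 20 subjects in one arm they can be read in full. No formal safety comparison is planned, so no test is affected. Much of the gap comes from the sparse schedule, and a new table row creates no data on days without a test. By-visit summaries on scheduled data are a coherent choice.

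What remains is narrow. Shift and threshold tables count abnormalities without relying on the Investigator's judgment, which is useful in an open-label, single-arm trial, and listings give no incidence. Neither the TEAE route nor the listings replaces that count.

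**Conclusion.** The point holds as a minor one. An abnormality seen only at an unscheduled test or repeat stays out of the laboratory and vital-sign shift and abnormal-change tables. It is visible in listings, and in the TEAE tables only through a judgment of clinical significance. The SAP also leaves open whether a repeat taken close to a scheduled visit counts as unscheduled, and which value then represents that visit.

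The size is 5 percentage points per affected subject, assuming a denominator of 20. How many subjects would be affected cannot be derived from the documents. The confidence bounds and the d/28 shares rest on the stated assumptions and are not forecasts.

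**What to change.** Keep the by-visit summaries on scheduled data. In SAP 6, 10.5 and 10.6:

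- Add worst-post-baseline rows to Tables 14.3.4.1.2 (hematology), 14.3.4.2.2 (chemistry), 14.3.4.3.2 (urinalysis, continuous parameters) and 14.3.5.1.2 (vital signs). Use all values after first dose, whether scheduled, unscheduled or repeat, and give the lowest and the highest value separate rows.
- For the vital-sign change thresholds, report the largest increase and the largest decrease separately. SAP 10.6 states these thresholds without a direction, so a single worst change would be undefined.
- Flag whether each worst value was obtained on treatment or after the last dose, so that the two periods are not mixed unseen.
- State which value represents a scheduled visit when a repeat was taken.
- Footnote that subjects tested more often have more chances of an abnormal value. With no comparator arm, the footnote discloses this effect but does not remove it.

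The cost is a little programming in four existing tables and possibly higher abnormal counts. No new visits, samples or clinical decisions are involved.
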